There are routine standard of care alternatives available; specify:

- Getting no treatment
- Getting standard treatment for your condition without being in a study.
- Getting a different experimental treatment/taking part in another study.

There are other alternatives to study participation; specify: <Type here>

SECTION 9: SUBJECT COSTS

1. Indicate below if subjects or their insurers will be charged for study procedures. Identify and describe those costs.

Not applicable: This study involves no interaction/intervention with research subjects. *Skip to Section 10.*

This study involves interaction/intervention with research subjects; however there are no costs to subjects/insurers.

This study involves interaction/intervention with research subjects, and there are costs to subjects/insurers:

2. If subjects or their insurers will be responsible for study-related costs, explain why it is appropriate to charge those costs to the subjects or their insurers. Provide supporting documentation as applicable (e.g., study procedures include routine (standard of care) procedures; FDA IDE/HDE/IND letter that supports billing to subjects).

Not applicable: The study involves no costs to subjects for study participation.

Study related costs will be billed to subjects or their insurers for the following reasons:

SECTION 10: SUBJECT COMPENSATION AND REIMBURSEMENT

1. If subjects will be compensated for their participation, explain the method/terms of payment (e.g., money; check; extra credit; gift certificate).

Not applicable: This study involves no interaction/intervention with research subjects. *Skip to Section 11.*

No compensation will be provided to subjects.

Compensation will be provided to subjects in the form of cash/gift certificate.

Compensation will be provided to subjects in the form of a check issued to the subjects through the UCI Accounting Office. The subject's name, address, and social security number, will be released to the UCI Accounting Office for the purpose of payment and for tax reporting to the Internal Revenue Service (IRS).

Other

2. Specify the schedule and amounts of compensation (e.g., at end of study; after each session/visit) including the total amount subjects can receive for completing the study. *Compensation should be offered on a prorated basis when the research involves multiple visits.*

For compensation $\geq \$600$, subject names and social security numbers must be collected. This information must be reported to UCI Accounting for tax-reporting purposes.

Not applicable: This study involves no compensation to subjects.

Subjects will be compensated with the following schedule and amounts:

3. Specify whether subjects will be reimbursed for out-of pocket expenses. If so, describe any requirements for reimbursement (e.g., receipt).

Not applicable: This study involves no reimbursement to subjects.

Subjects will be reimbursed; specify:

SECTION 11: CONFIDENTIALITY OF RESEARCH BIOSPECIMENS/DATA

A. Biospecimens/Data Storage

1. Indicate all subject identifiers that may be included with the biospecimens or collected for the research study. *If any study-related data will be derived from a medical record, added to a medical record, created or collected as part of health care, or used to make health care decisions the HIPAA policy applies. The subject's HIPAA Research Authorization is required or a waiver of HIPAA Research Authorization must be requested by completing Appendix T.*

This study does not involve the collection of subject identifiers.

Check all the following subject identifiers will be used, created, collected, disclosed as part of the research:

 Names	 Social Security Numbers	 Device identifiers/Serial numbers
 Dates*	 Medical record numbers	 Web URLs
 Postal address	 Health plan numbers	 IP address numbers
 Phone numbers	 Account numbers	 Biometric identifiers
 Fax numbers	 License/Certificate numbers	 Facial Photos/Images
 Email address	 Vehicle id numbers	 Any other unique identifier
 Other (Specify all): <Type here>		

* *birth date, treatment/hospitalization dates*

Indicate how data will be stored and secured, including electronic data as well as hardcopy data paper records, electronic files, audio/video tapes, biospecimens, etc. *If the research data includes subject identifiable data and/or Protected Health Information, the storage devices or the electronic research files must be encrypted. [For guidance on the use of cloud services, please review the [UCI OIT policy](#).]*

Electronic Data/Files (check all that apply):

- [] Anonymous data will be maintained; no subject identifiers
- [X] Coded data; code key is kept separate from data in secure location.
- [] Data includes subject identifiable information. Provide rationale for maintaining subject identifiable info): <Type here>
- [X] Data will be stored on secure network server.
- [] Data will be stored on standalone desktop computer (not connected to network/internet)
- [] Other (specify here): <Type here>

Hardcopy Data (Records, Recordings, Photographs) and Biospecimens (check all that apply):

- [] Anonymous biospecimens/data will be maintained; no subject identifiers
- [X] Coded data; code key is kept separate from biospecimens/data in secure location.
- [] Biospecimens/Data includes subject identifiable information (Provide rationale for maintaining subject identifiable info): <Type here>
- [X] Data will be stored in locked file cabinet or locked room.
- [] Biospecimens will be stored in locked lab/refrigerator/freezer.
- [] Other (specify here): <Type here>

2. List the location(s) where the data and/or biological specimens will be stored.

The data will be stored in a secure, locked facility in the UCI Anesthesia Research Department for the duration of the study approval. Only, the investigators and study personnel will have access to the data. Any data collected on the computer will only be stored on a secure, encrypted server. Data will be retained for six years as this research involves Protected Health Information.

3. If subject identifiable data will be transported or maintained on portable devices, explain why it is necessary use these devices. *Only the “minimum data necessary” should be stored on portable devices as these devices are particularly susceptible to loss or theft. If there is a necessity to use a portable device for the initial collection of identifiable private information, the research files must be encrypted, and subject identifiers transferred to a secure system as soon as possible.*

[X] Not applicable: Research data will not be transported or maintained on portable devices.

Research data will need to be maintained on the following portable device(s) for the following reason(s): <Type here>

B. Data and/or Biological Specimens Access

Specify who will have access to subject identifiable data and/or biological specimens as part of this study.

Not applicable: No subject identifiers will be collected.

Authorized UCI personnel such as the research team and appropriate institutional officials, the study sponsor or the sponsor's agents (if applicable), and regulatory entities such as the Food and Drug Administration (FDA), the Office of Human Research Protections (OHRP), and the National Institutes of Health (NIH).

Other: <Type here>

C. Data and/or Biological Specimens Retention

Indicate how long subject identifiable data and/or biological specimens, including the subject code key will be retained. *If more than one of the options below is applicable (e.g., the study involves children), records must be kept for the longer period.*

Not applicable: No subject identifiable research data will be retained.

Separate code key will be destroyed or subject identifiable information will be removed from the biospecimens and/or data at the earliest convenience, consistent with the conduct of this research. Specify timeframe: <Type here>

Destroyed once research data is analyzed.

Destroyed after publication/presentation.

Will be maintained; specify time frame and provide the rationale: <Type here>

Will be stored and maintained in a repository for future research purposes.

Complete Appendix M

Will be retained for six years as this research involves Protected Health Information (PHI) (e.g., IRB documentation, consent/assent forms – NOT the actual PHI). *Investigators must destroy PHI at the earliest opportunity, consistent with the conduct of this study, unless there is an appropriate justification for retaining the identifiers or as required by law.*

Will be retained for seven years after all children enrolled in the study reach the age of majority [age 18 in California] as this study includes children.

Will be retained 25 years after study closure as this study involves in vitro fertilization studies or research involving pregnant women.

Will be retained for two years after an approved marketing application, as this is a FDA regulated study. If approval is not received, the research records will be kept for 2 years after the investigation is discontinued and the FDA is notified.

Other: <Type here>

D. Photographs, Audio/Video Recordings Retention

1. If subject identifiable audio or video recordings will be collected, specify the timeframe for the transcription and describe retention/destruction plans.

Not applicable: Subject identifiable audio/video recordings will not be collected.

Audio or video recordings transcribed; specify time frame: <Type here>

Audio or video recordings will be maintained; specify time frame: <Type here>

Audio or video recordings maintained indefinitely; provide the rationale: <Type here>

Audio or video recordings destroyed; specify time frame: <Type here>

2. If subject identifiable photographs will be collected, describe retention/destruction plans.

Not applicable: Subject identifiable photographs will not be collected.

Photographs will be maintained; specify time frame: <Type here>

Photographs maintained indefinitely; provide the rationale: <Type here>

Photographs destroyed; specify time frame: <Type here>

E. Certificate of Confidentiality

1. Indicate whether a Certificate of Confidentiality (COC) has been or will be requested.

Not applicable: No COC has been requested for this study.

A COC will be or has been requested for this study. *The COC application must be submitted to the IRB staff for review after IRB approval.*

A COC has been obtained for this study. The expiration date of this COC is: <Type here>

Provide a copy of the COC Approval Letter.

2. Explain in what situations the UCI study team will disclose identifiable private information protected by a COC.

<Type here>

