The significance of this study is to evaluate the efficacy of OnabotulinumtoxinA (BOTOX®) for the treatment and prophylaxis of pediatric migraine in a randomized, double-blinded, placebo cross over study. No trials currently exist in literature studying OnabotulinumtoxinA for efficacy and/or safety for indication of pediatric migraine, although significant contributions have been made by retrospective case series over the last 10 years. The historical and longitudinal context of the interest to design this study comes from the Principal Investigator's (PI) extensive use of "off label" OnabotulinumtoxinA to treat refractory pediatric migraine over the last 5 years. Anecdotally, the results are so impressive and impactful in her patients' lives, that this therapeutic ought to be studied in a controlled setting to demonstrate clinical outcome to validate existing treatment strategies. Thus, this study seeks to fulfill ASRA's goal of identification of novel applications of existing therapeutics. Moreover, this trial may benefit an under-studied pain population with the long-term goal of new FDA indication to "on label" status. The proposal also carries policy and legislative impact as it fulfills the federal initiative to design and conduct trials in the pediatric pain population within confines of the Best Pharmaceuticals for Children Act (BPCA) of 2002. The goal of the BPCA Program is to improve pediatric therapeutics through preclinical and clinical drug trials that lead to drug labeling changes.

3. Describe the purpose, specific aims or objectives. Specify the hypotheses or research questions to be studied.

Specific Aims

The proposed research is intended to explore whether pediatric chronic migraine may benefit from OnabotulinumtoxinA treatment. The study is focused on a specific debilitating disorder of chronic pain in a well-defined population that is historically not well studied. The objectives are attainable within the proposed timeframe.

Hypothesis:

Aim 1: To test if OnabotulinumtoxinA is superior to placebo in reducing headache frequency, intensity and pediatric migraine-related disability (Efficacy)

Aim 2: To evaluate the incidence of adverse events of OnabotulinumtoxinA administration in children aged 8-17 (Safety, Tolerability)

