Specify where the research procedures will take place (e.g. UCI Douglas Hospital – Cardiac Care Unit, UCI Main Campus Hewitt Hall, UCI Health – Pavilion II, UCI Family Health Center, Anaheim, Irvine High School).

If research activities will also be conducted at non-UCI locations (e.g., educational institutions, businesses, organizations, etc.), Complete Appendix A. Letters of Permission or other documentation may be required (e.g. Off-site Research Agreements or IRB Authorization Agreements).

The research procedures will take place at UC Irvine Medical Center in the Medical Specialties facility and Gottschalk Medical Plaza on UCI main campus. Any data obtained for the study will be stored in a secure, locked facility in the UCI Anesthesia Research Department for the duration of the study.

B. Study Design

1. Include an explanation of the study design (e.g., randomized placebo-controlled, cross-over, cross-sectional, longitudinal, etc.) and, if appropriate, describe stratification/ randomization/blinding scheme.

Study Protocol

After enrollment, each subject will begin with a 28 day baseline screening phase followed by a 24 week double-blind, placebo-controlled, randomized AB|BA crossover period as the primary study protocol, followed by a second 24-week open-label period where all subjects will receive treatment with OnabotulinumtoxinA as follow-on treatment. There will be one treatment every 12 weeks, meaning 4 treatment blocks over the 48 week study period total. Those assigned to the AB group will receive OnabotulinumtoxinA in the first treatment and saline placebo in the second, while those in the BA group will receive saline and then OnabotulinumtoxinA. Both groups will then receive OnabotulinumtoxinA in the last two treatments. Progress check-ups will occur every 6 weeks during the study. Twelve week blocks were specifically selected in order to minimize carry-over effects from treatment periods, as the clinical efficacy of OnabotulinumtoxinA is nearly gone after twelve weeks in the PI's experience and reported literature.

Randomization will be via selection of sealed envelope. Injections will be performed at fixed-site, fixed-dose locations at 31 sites recommended by the PREEMPT 1 and 2 studies, including procerus, corrugators, frontalis, temporalis, occipitalis, splenius capitis, and trapezius muscle beds. At the

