investigator's discretion, an additional 40U may be administered using a follow-the-pain strategy. The maximum dose will be **155 U across 31 sites**. All treatments will be performed by the PI.

2. Provide precise definitions of the study endpoints and criteria for evaluation; if the primary outcomes are derived from several measurements (i.e., composite variables) or if endpoints are based composite variables, then describe precisely how the composite variables are derived.

Primary outcome variables:

- Pain scores: as a standard part of the procedure, patients are asked to record their pain scores before and after their procedure. The principal endpoints are intensity on a 10 point NRS scale (VAS where needed), and frequency of migraine episodes in a 30 day period. This will be compared to baseline data pre-injection. For the study, pain score data will be collected up until the last follow up of the last injection of each patients' Botox ® injection series.
- Duration of benefit from the Botox ® injections: reduction in pain score by greater than or equal to 30%
- Functionality: the extent of normal activity able to be performed by a patient
- Disability: inability to function normally, physically or mentally
- Opioid consumption: amount of opioid medication consumed
- Neuropathic/migraine medication consumed including immediate release NSAID

Secondary outcome variables:

- Quality of pain: continuous, intermittent, throbbing, etc.
- Associated side effects: nausea, vomiting, food intake, diarrhea, constipation, anxiety, depression and/or adverse events associated with study drug
- Psychological history i.e. anxiety, depression
- Neuropathy: any weakness, numbness, and pain from nerve damage, usually in the hands and feet
- Type of analgesia/anesthesia: analgesic/anesthetic medication(s) used during procedure

Incidence of hospital admissions

- Incidence of ER visits
- Current medication use

Other variables:

- Neurological workup: Neurological medical evaluation, including medical history, physical examination, medical tests, survey of the patient's medical record for any information regarding Neurological disease
- Diagnosis: identification of chronic migraine head pain
- Indications: reason for Botox ® injections, number of injections in the Botox ® injection series
- Procedure: specific procedure including location of procedure, imaging information, and other specific procedure information

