- Block medications: medications and dosage used for the Botox ® injections
- Disposition: notes regarding patient's state during procedure

[figure not shown]
C. Research Procedures

1. Provide a detailed chronological description of all research procedures.

Methods

Given the existing evidence of efficacy in the available scientific data (adult and retrospective pediatric) and the PI's extensive personal experience in the pediatric population (where use of the study drug has

been found to be transformative), prolonged withholding of OnabotulinumtoxinA for the purpose of study was not considered reasonable by the PI. Thus, a study design minimizing the placebo control period while still allowing for comparison of OnabotulinumtoxinA to a control group, was desirable. An AB|BA cross-over design (which uses each patient has his/her own control, both minimizing recruitment numbers and the need for a control group which never receives treatment with OnabotulinumtoxinA), was selected as the best option after consultation. The influence of confounding covariates is reduced because each crossover patient serves as his or her own control. A four week baseline prior to treatment will act as a no-treatment control to compare to both the treatment and placebo. The study does not exclude patients on preventive or abortive migraine medication, in an attempt to demonstrate superiority on study drug over conservative medical management.

Diagrams 1-4: Recommended Injection Sites (A through G) for Chronic Migraine

(From BOTOX® Prescribing Information) Total of 31 Sites with a **maximum dose will be 155 U**

All data collection will follow Good Clinical Practices and HIPPA. This study has been submitted to the Institutional Review Board. Parent/guardian and/or child will sign an informed consent and assent (child) approving enrollment in study.

Patient Population

Children aged 8 – 17 years of age with a history of migraine meeting the criteria established in ICHD-II (2004), Section 1. Patients will provide at least 28-days (4 week) baseline data in the form a daily diary and must have at least 15 days of reported headache during this period, with at least 4 distinct episodes lasting at least 4 hours each. (Patients with continuous headache will thus be excluded as this may represent non-migraine symptoms). A total of 26 patients will be enrolled.

Data Collection

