1. Describe and assess any reasonably foreseeable risks and discomforts — physical, psychological, social, legal or other. Include an assessment of their expected frequency (e.g., common – 65%, less common – 40%, unlikely – 5%, rare - <1%) and the seriousness (mild, moderate, severe). A *bullet point list is recommended. If this study will involve the collection of identifiable private information, even temporarily, for which the disclosure of the data outside of the research could reasonably place the subjects at risk, include the risk of a potential breach of confidentiality.*

As listed in the Risks section of the Informed Consent.

2. Discuss what steps have been taken and/or will be taken to prevent and minimize any risks/ potential discomforts to subjects. *Examples include: designing the study to make use of procedures involving less risk when appropriate; minimizing study procedures by taking advantage of clinical procedures conducted on the subjects; mitigating risks by planning special monitoring or conducting supportive inventions for the study; implement security provisions to protect confidential information.*

All extracted data will be de-identified immediately and save on a secured database for research purposes only. Study team members will follow strictly the reporting guideline by IRB in case of a breach of confidentiality, which is nearly impossible since all data are de-identified. Regardless, all collected information will be securely stored on a password-protected server.

Subjects for this study will be closely monitored for any potential adverse events. Subjects will be able to call the Lead Researcher 24 hours a day for any potential issues.

C. Potential Benefits

1. Describe the potential benefits subjects may expect to receive from participation in this study. *Compensation is not a benefit; do not include it in this section.*

There is no direct benefit anticipated for the subjects.

There is a prospect of direct benefit to children participating in the study. Taking part in this study may or may not make your health better with the first two treatments. While researchers hope Botox® will be more effective than the standard (usual) treatment, there is limited proof of this yet.

2. Specify the expected potential societal/scientific benefit(s) of this study.

Overriding Rationale

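### Section 6 permits an extra 40 U at the investigator's discretion, then sets a 155 U maximum without saying whether the maximum includes it

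*Combined protocol and SAP*

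**What the plan says.** Three statements bear on the dose given at each treatment.

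- Section 6.B.1 (Study Design) sets the scheme: "Injections will be performed at fixed-site, fixed-dose locations at 31 sites recommended by the PREEMPT 1 and 2 studies". It names the muscle groups but gives no dose per site and no base total.
- The same paragraph continues that, at the investigator's discretion, "an additional 40U may be administered using a follow-the-pain strategy". It does not say whether this goes into the 31 sites or into others.
- The sentence after that gives the maximum as "155 U across 31 sites".

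Section 6.C.1 (Methods) returns to the point in the caption headed "Diagrams 1-4: Recommended Injection Sites (A through G) for Chronic Migraine". The caption again gives 31 sites and says the "maximum dose will be 155 U". It does not mention the addition.

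Two other places give the context. Aim 2 in Section 1, item 3 is "To evaluate the incidence of adverse events of OnabotulinumtoxinA administration in children aged 8-17". Section 7.B.1, which asks for the foreseeable risks, answers only "As listed in the Risks section of the Informed Consent".

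**The concern.** One sentence authorises an amount described as additional to a fixed scheme. The next sets a maximum that, on the only base dose its own figures suggest, leaves no room for that amount. The text does not say which sentence governs, or whether they describe different things (the fixed sites on the one hand, the whole treatment on the other).

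The practical consequence is that the PI, the IRB or a monitor cannot settle from the written protocol whether a treatment that included the addition was compliant or a deviation. The rule applies at each of four treatments per child, three of them active in either sequence. The study is marked in Section 7.A as greater than minimal risk. Adverse events are a stated aim, and they are hard to interpret against exposure when the permitted exposure is not defined. Because Section 7.B.1 defers to the consent form, that form also needs a single protocol ceiling to match.

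**Working it through.** **Inputs.** From Section 6.B.1: 31 sites, an optional 40 U, and a maximum of 155 U. From the caption in Section 6.C.1: 31 sites and 155 U again. The base total, meaning the dose in the 31 sites before any addition, is not stated, so it is treated as an unknown B.

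**Step 1: the base that the figures suggest.** 155 / 31 = 5.00 U per site exactly. This makes it natural to read 155 U as the full fixed-site total, but it is an inference from division and not something the text states.

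**Step 2: the maximum covers the whole treatment.** With the full addition the total is B + 40, and the excess over the maximum is B + 40 − 155 = B − 115.

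| Base B | Average per site (B/31) | Total with 40 U | Excess over 155 U |
|---|---|---|---|
| 155 U (inferred) | 5.00 U | 195 U | 40 U (40/155 = 25.8%) |
| 135 U (illustrative only) | 4.35 U | 175 U | 20 U (20/155 = 12.9%) |
| 115 U (break-even) | 3.71 U | 155 U | 0 |

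The permission and the ceiling can therefore both hold in full only if the base is 115 U or less, and no such base is stated. Because the scheme is described as fixed-dose, the base cannot simply be lowered in a given child to make room.

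Under this same scope, a reader may decide that the maximum overrides the permission. On a 155 U base the usable addition is then 155 − 155 = 0 U, and the sentence granting it has no effect.

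**Step 3: the maximum covers only the 31 fixed sites.** There is no excess. The implied upper total is 155 + 40 = 195 U, but the reader has to construct it. The protocol states no overall ceiling, and the caption in Section 6.C.1 shows only 155 U.

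**Step 4: what could not be seen.** One figure and the injection-site diagrams are not shown, a part of the document ahead of Section 3 was not available, and the consent form is not in the file. A diagram might supply per-site doses and so fix B. Its visible caption does not say whether 155 U includes the addition.

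The protocol does not say how often the addition would be used, so no trial-wide figure is computed.

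**The case against.** The strongest reply is that a ceiling is stated, twice and with emphasis, and directly after the permission. In ordinary usage a maximum that follows a permission limits it, so any treatment above 155 U would be a deviation and a monitor could say so. The 40 U sentence might then be no more than leftover wording. This is a fair literal reading, but it does not remove the defect. On a 155 U base it makes an express authorisation empty, and nothing in the current text marks that sentence as superseded. Nor can a reader assume that totals above 155 U were never in view: the background in Section 1 cites a paediatric series with an average dose of 188.5 ± 32 units.

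Several narrower points stand. The reading in which the ceiling is breached and the reading in which it overrides the permission share the same scope and differ only in which sentence prevails. If the maximum is confined to the fixed sites, 195 U follows by addition, so the dose is not open-ended; what is missing is a stated total. The 135 U case has no source in the documents and serves only to show the range. No mismatch with the consent form has been shown, because the form was not available.

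There is also mitigation. This is a single-site study, the PI gives every treatment, and Section 6.B.2 lists the dosage used among the recorded variables. Differences between injectors are therefore not a concern, and the delivered dose should be known. Recording the dose still does not supply an unambiguous limit to check it against.

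**Conclusion.** The concern holds. The discretionary addition and the stated maximum are not reconciled anywhere in the text available, and this should be corrected before the dose rule is relied on. Confidence in the inconsistency itself is high.

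Its size is conditional. The figures of 195 U and 40 U (25.8%) over the maximum require both a 155 U base, which is inferred, and a maximum that covers the whole treatment. With that scope the conflict exists for any base above 115 U and vanishes at or below it. With a maximum confined to the 31 sites there is no excess, only a missing overall ceiling.

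The point does not touch the primary endpoint, its analysis or the sample size. Its weight comes from its being a dose limit in children, in a trial that sets out to measure adverse events.

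**What to change.** Reconcile the Study Design paragraph in Section 6.B.1 with the caption in Section 6.C.1 so that together they give:

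- one injection scheme with its base total;
- one overall ceiling per treatment;
- an explicit statement of whether that ceiling includes the discretionary addition and, if the addition is kept, whether it goes into the 31 sites or elsewhere.

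Then check that the injection-site diagrams and the consent form agree with the reconciled text. Which dose rule is right is for the study team and the IRB to decide; this review takes no position on it.

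The cost is a short protocol correction submitted to the IRB, with no new data collection and no change to the sample size.
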